## 1.2 Study design

### 1.2.1 Overall Design

This is a multi-center, open-label Phase 1B study to assess the PK, safety, and tolerability of CZP in adults with active RA. In this 24-week study, study participants (ie, male or female participants 18 to 69 years of age inclusive) who are naïve to CZP and are eligible to receive a biologic for RA will receive CZP in subcutaneous (sc) loading doses at Weeks 0,

---

2, and 4, followed by a treatment of 200mg every 2 weeks (Q2W), with the final dose taking place at Week 24.

### **1.2.2 Number of Participants**

A total of 30 participants will be enrolled to receive CZP, such that a minimum of 25 evaluable participants are expected to complete Visit 13 (Week 12).

[figure not shown]
### **1.2.3 Treatment Groups and Duration**

All study participants will receive CZP treatment. Study participants may be taking concomitant methotrexate (MTX); however, a minimum of 8 study participants must be enrolled who are not on concurrent administration of MTX.

The duration of the study is approximately 38 weeks. The study consists of a Screening Period (28 days), Baseline Visit, a Treatment Period (24 weeks), and a Safety Follow-up (SFU) Visit (70 days after the last study visit).

PUBLIC COPY  
This document cannot be used to support any marketing authorization application and any extensions or variations thereof.

### 1.2.4 Schema- Schedule of Activities

ADAb=antidrug antibody; BL=Baseline; CZP=certolizumab pegol; PK=pharmacokinetic; Q2W=every 2 weeks; W=week  
a CZP naïve at enrollment.

## 2 STATISTICAL HYPOTHESES

No formal statistical hypothesis testing is planned in this study.

## 3 SAMPLE SIZE DETERMINATION

With no formal hypothesis testing, a sample size of 30 enrolled participants with 25 participants who completed Visit 13 is deemed to provide sufficient plasma CZP concentration data with the ECLIA analytical method to serve as a reference PK dataset for PK matching in the pJIA program. Further, a simulation and re-estimation method applied using a non-RA CZP population PK model indicated that a sample size of 25 participants who completed Visit 13 in a study with the PK sampling scheme as that presently planned can estimate absorption rate constant, clearance, and distribution volume with acceptable precision (relative standard deviation of <16%). Participants who withdraw from the study may be replaced at the discretion of the Investigator and Sponsor, depending on the circumstances.

## 4 POPULATIONS FOR ANALYSIS

The following analysis sets will be used in the study:

- All Study Participants (ASP) will include those study participants who are confirmed as having signed the ICF form to participate in the study.
- The Safety Set (SS) will include all study participants enrolled who receive  $\geq 1$  injection of study medication. Safety variables will be summarized using the SS.
- The Pharmacokinetic Set (PKS) is a subset of the SS, consisting of study participants who have provided plasma samples with measurable concentrations (with recorded sampling time) on at least 1 visit, and who have no important protocol deviations affecting the PK parameters.

## 5 STATISTICAL ANALYSES

### 5.1 General Considerations

Statistical analysis and generation of tables, figures, and study participant data listings will be performed using statistical analysis system (SAS®, SAS Institute, Cary, NC, US) version 9.3 or higher using validated program code according to relevant standard operating procedures. PK parameters will be calculated by Non-Compartmental Analysis (NCA) methods from the concentration-time data with actual time using Phoenix® WinNonlin® Version 8.3 or higher following UCB guideline: Guideline on performing NCA analysis, Nov 2017.

In general, there will be no imputation of missing data unless otherwise stated.

For categorical parameters, the number and percentage of study participants in each category will be presented. The denominator for percentages will be based on the number of study participants appropriate for the purpose of the analysis. For continuous parameters, descriptive statistics will include number of study participants, arithmetic mean, standard deviation, median, minimum, and maximum (with 25th and 75th percentiles as optional).

Baseline is defined as the last nonmissing measurement collected before the first injection.

When reporting relative frequencies or other percentage values, the following rules apply:

- For values where all study participants fulfill certain criteria, the percentage value will be displayed as 100

- For values where the absolute frequency is zero, there will be no percentage displayed at all
- All other percentage displays will use 1 decimal place

Percentages displayed based on continuous data (eg, percentage changes from baseline) will be displayed to 1 decimal place.

When reporting descriptive statistics, the following rules will apply in general:

- n will be an integer
- Mean (arithmetic and geometric), SD and median will use 1 decimal place more than the original data
- geoCV will be reported as a percentage to 1 decimal place
- Minimum and maximum will be reported using the same number of decimal places as the original value
- If no study participants have data at a given time point, for example, then only n=0 will be presented. If n<3, then only n, minimum and maximum will be presented. If n=3, then only n, mean, median, minimum and maximum will be presented. The other descriptive statistics will be left blank.

For CZP plasma concentration, the geometric mean and corresponding coefficient of variation will be presented. The geometric coefficient of variation (CV) is calculated as  $\sqrt{(\exp(\text{std ln}^2) - 1)} * 100$ , where std ln is the standard deviation of the log-transformed data.

All tabulations will be performed for PKS, visit and timepoint (where applicable). Data listings containing all documented data and all derived data will be generated.

### **5.1.1 General study level definitions**

#### **5.1.1.1 Analysis Time Points**

##### **5.1.1.1.1 Relative day**

Relative day for an event will be derived with the date of the first sc injection of study drug as reference.

Relative days for an event or measurement occurring before the date of the sc injection of study drug are calculated as follows:

$$\text{Relative Day} = [(\text{Event Date} - \text{Date of First Injection})]$$

The relative day for an event or measurement occurring on or after the reference date to the date of the sc injection is calculated as follows:

$$\text{Relative Day} = [(\text{Event Date} - \text{Date of First Injection}) + 1]$$

In the listing, Relative Day will be presented as below: numbers with no prefix are days after first dose at visit 2 +1, '-' prefixed numbers are days before first dose at visit 2 and '+' prefixed numbers will be days after last dose at visit 15.

For PK, the relative time (hour) is calculated as the date time of each sample minus the date time of dose at the PK sample date.

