^b Home Visits may occur at the clinic/site rather than at home per study participant preference. Assessments at Home Visits will be conducted by the Home Visit nurse.

^c In WOCBP, at Screening, a serum pregnancy test will be performed; for subsequent visits, urine pregnancy tests will be performed according to the Schedule of Activities.

^d All ECG recordings should be taken with the study participant resting in the supine position for at least 5 minutes before the recording.

^e Loading doses of 400mg CZP will be administered at Weeks 0, 2, and 4, followed by treatment with 200mg Q2W. Study participants will have the option to self-inject IMP at home on Weeks 14, 16, 20, and 22.

^f At Visits in which dosing will take place, all activities should take place prior to IMP administration (including PK collection).

^g PK profile samples to be collected at 2 (Visit 9), 5 (Visit 10), 7 (Visit 11) and 10 (Visit 12) days post-Week 10 IMP administration.

PUBLIC COPY
This document cannot be used to support any marketing authorization application and any extensions or variations thereof.

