8.6 Pharmacokinetics

Pharmacokinetic samples will be tested using the ECLIA method. All PK assessments will be evaluated as described in the Schedule of Activities (Section 1.3).

Whole blood samples of approximately 5 mL will be collected for measurement of plasma concentrations of CZP as specified in the Schedule of Activities (Section 1.3). A maximum of 3 samples may be collected at additional time points during the study if warranted and agreed upon between the Investigator and the Sponsor. Instructions for the collection and handling of biological samples will be provided by the Sponsor. The actual date and time (24-hour clock time) of each sample will be recorded.

Samples will be used to evaluate the PK of CZP. Samples collected for analyses of CZP (plasma/serum/whole blood) concentration may also be used to evaluate safety or efficacy aspects related to concerns arising during or after the study.

Genetic analyses will not be performed on the plasma or whole blood samples.

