9.3.1 Other analyses

9.3.1.1 Pharmacokinetic analyses

Pharmacokinetic analysis will be performed on the PKS population.

Concentration-time profiles will be summarized by visit, and descriptive statistics performed, including: n, geometric mean, CV%, maximum, minimum, arithmetic mean, and standard deviation.

A PK analysis will be performed to derive noncompartmental CZP PK parameters (C_{min} and AUC) after their Week 10 dose. If needed, additional PK parameters may be derived based on the data. Further details of the analysis will be specified in the Statistical Analysis Plan.

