#### 5.1.1.1.3 Study periods

The duration of the study for each study participant is approximately 38 weeks.; consisting of the following 3 periods:

- Screening Period (up to 28 days): Visit 1, Day -28 to Day -1
- Treatment Period (24 weeks) including Baseline visit: based on the first planned treatment starting from Visit 2 at Day 0 to the last planned treatment on Visit 15 at Day 168 (Week 24)
  - 400mg loading dose phase for doses at Week 0, Weeks 2 and 4 followed by 200mg Q2W maintenance dose phase thereafter (at Week 6, 8, 10, 12, 14, 16, 18, 20, 22 and 24)
  - PK profile treatment Period: Day 72±6 hours to Day 80±6 hours. These visits may be conducted at home visit.
- Safety Follow-Up: The end of study visit will be performed on 70 days after last IMP through SFU visit.

The end of the study is defined as the date of the last visit of the last study participant in the study. Study participants are considered to have completed the study if they complete the last scheduled study visit (Screening, Baseline Visit, Treatment Period [through Week 24], and SFU). The safety follow-up visit is 70 days post last dose. If study participants are continuing onto commercial Cimzia, the safety follow-up is 30 days post last dose.

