#### 5.3.2 Main analytical approach

The primary PK parameters in plasma are:  $C_{min}$  and  $AUC_{0-\tau}$ .

The primary PK parameters of CZP will be summarized by MTX use at screening using descriptive statistics (number of available observations ( $n$ ), arithmetic mean, median, SD, minimum, maximum, geometric mean, geometric CV and 95% CI for the geometric mean (assuming lognormally distributed data)). Values below the LLOQ will be reported with a clear sign indicating that they were below the LLOQ.

For calculation of the PK data (including parameter), the actual blood sampling times will be used.

All PK data will be listed and summarized for all study participants for the PKS including  $n$ , arithmetic mean, median, SD, minimum, maximum, geometric mean, geoCV and 95% CI for the geometric mean.

The following rules will apply for the PK data summaries:

- PK parameters are reported with 3 significant digits and Descriptive statistics reported to 4 significant figures for the mean, median and standard deviation (SD) and to 3 significant figures for all others.
- Values below the LLOQ will be reported as BLQ for individual data and will be substituted with  $LLOQ/2$  for the descriptive statistics
- Descriptive statistics of PK concentrations will be calculated only if at least  $\frac{2}{3}$  of the individual data at a specific sampling timepoint are measured and are quantifiable (ie, above LLOQ) and if  $n \geq 4$ . If  $n < 3$ , then only  $n$ , minimum and maximum will be presented and if  $n = 3$ , then only  $n$ , median, minimum and maximum will be presented and the other descriptive statistics will be left blank.
- Descriptive statistics of PK parameters will be calculated only if at least  $\frac{2}{3}$  of the individual data are calculable and if  $n \geq 4$ . If  $n < 3$ , then only  $n$ , minimum and maximum will be presented and if  $n = 3$ , then only  $n$ , median, minimum and maximum will be presented and the other descriptive statistics will be left blank.

- If no study participants have data, only n=0 will be presented.
- The 95% lower and upper CI should be left blank if the SD (or equivalently the geoCV) is equal to 0
- The geoCV will be calculated using the following formula where SD is the standard deviation of the log-transformed values:  $\text{geoCV} (\%) = \sqrt{(\exp(\text{SD}^2) - 1)} \times 100$

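### The SAP's PK relative-time formula is wrong for the primary Week 10 to 12 profile: four of six samples get no time and the Day 84 sample lands at about 0 h (low severity, one sentence to replace)

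*SAP*

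**What the plan says.** **Timing rule.** SAP 5.1.1.1.1 (Relative day) ends with the only PK time formula in the SAP: "the relative time (hour) is calculated as the date time of each sample minus the date time of dose at the PK sample date". SAP 5.5.1.1.2 also promises a time since administration, in days, for a joint concentration and antibody listing, but gives no formula and names no reference dose.

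**Dosing and sampling.** SAP 5.1.1.1.3 gives the loading doses and then: "followed by 200mg Q2W maintenance dose phase thereafter (at Week 6, 8, 10, 12, 14, 16, 18, 20, 22 and 24"). The Schedule of Activities (Protocol 1.3) places plasma samples on Days 70, 72, 75, 77, 80 and 84 (Visits 8 to 13). Footnote f fixes the order on dosing days: "At Visits in which dosing will take place, all activities should take place prior to IMP administration (including PK collection").

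**Reference dose in the protocol.** Footnote g reads: "PK profile samples to be collected at 2 (Visit 9), 5 (Visit 10), 7 (Visit 11) and 10 (Visit 12) days post-Week 10" IMP administration. Protocol 9.3.1.1 derives Cmin and AUC "after their Week 10 dose".

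**NCA time basis in the SAP.** SAP 5.1 states: "PK parameters will be calculated by Non-Compartmental Analysis (NCA) methods from the concentration-time data with actual time". SAP 5.3.2 adds: "For calculation of the PK data (including parameter), the actual blood sampling times will be used". Neither names the dose from which time is counted. SAP 5.3.1 defines AUC0-tau over one dosing interval. SAP 5.1 refers NCA method to a sponsor guideline that is not among the documents.

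**The concern.** The formula needs a dose on the date of the sample. With dosing every two weeks, the samples between two doses have no such dose. A sample drawn just before the next dose is tied to that next dose, not to the one whose exposure it measures. Both problems arise in the Week 10 to 12 profile.

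AUC0-tau from this profile is one of the two primary PK parameters, and the study exists to supply an adult reference for PK matching in the pJIA program. An analyst who builds the time variable from SAP 5.1.1.1.1 would have to override the stated rule to obtain a usable profile. The rule also disagrees with the protocol on which dose the profile is timed from.

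**Working it through.** **Inputs**
- Profile sampling days: 70, 72, 75, 77, 80, 84 (Schedule of Activities).
- Doses near the profile: Weeks 8, 10 and 12, that is Days 56, 70 and 84 (SAP 5.1.1.1.3), with none in between.
- Samples on Days 70 and 84 are pre-dose (footnote f).

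**Step 1. Reproduce the protocol's own figure.** Sample day minus Day 70 gives 72 − 70 = 2, 75 − 70 = 5, 77 − 70 = 7 and 80 − 70 = 10 days. These match footnote g, so the profile is meant to run from the Week 10 dose.

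**Step 2. Apply the SAP formula and its possible readings.** Nominal hours = 24 × (sample day − reference dose day).

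| Sample day | Dose on the same date (as written) | Latest dose dated on or before the sample date | Latest dose actually given before the sample | Week 10 dose (protocol) |
|---|---|---|---|---|
| 70 | about 0 | about 0 | 24 × (70 − 56) = 336, after Week 8 | about 0 |
| 72 | none | 48 | 48 | 48 |
| 75 | none | 120 | 120 | 120 |
| 77 | none | 168 | 168 | 168 |
| 80 | none | 240 | 240 | 240 |
| 84 | about 0 | about 0 | 336 | 336 |

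As written, four of six samples have no time, and Day 84 is about 336 h too early. Strictly, the two values of about 0 h are slightly negative, because both samples precede that day's injection. The two samples that do get a time coincide, so the time span is about zero.

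The looser readings in columns three and four do better, but neither times both boundary samples correctly. One puts Day 84 at the wrong end of the interval; the other does the same to Day 70.

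**Step 3. Check whether the AUC itself depends on the time origin.** Trapezoid widths are differences between sample times.
- From the Week 10 dose (0, 48, 120, 168, 240, 336 h), the widths are 48, 72, 48, 72 and 96 h. Sum: 48 + 72 + 48 + 72 + 96 = 336 h.
- From the first dose (24 × day: 1680, 1728, 1800, 1848, 1920, 2016 h), the widths are again 48, 72, 48, 72 and 96 h. Sum: 336 h.

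Any one origin used for all six samples gives the same widths. The defect is that SAP 5.1.1.1.1 changes the origin from sample to sample, and for four of them has none.

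**Step 4. Check whether the right times can be recovered.** Protocol 8.6 states: "The actual date and time (24-hour clock time) of each sample will be recorded". SAP 5.6.1 lists the date and time of every administration. Both terms of the subtraction are therefore available.

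**The case against.** The strongest reply is that this sentence does not govern the AUC. It closes a section on relative days, just after rules for how days appear in listings, and neither SAP 5.1 nor 5.3.2 points to it. Those sections run the NCA on actual sampling times. The SAP presupposes the protocol, which names the Week 10 dose. Trapezoid widths need only a common origin, and the sponsor's NCA guideline may define time after dose.

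Most of this stands, and it removes the larger conclusions a reader might draw:
- *AUC0-tau cannot be derived or reproduced.* The documents do not support this. The reference dose can be found in the protocol, the times are recorded, and the guideline has not been seen.
- *The reported AUC will be biased.* The documents do not show this. A rule that leaves four of six samples untimed fails openly.
- *Up to 96/336 = 28.6% of the AUC is at risk, because the last interval rests on Day 84.* That figure is a share of clock time, not an AUC error, and no rule drops the Day 84 sample.
- *Other PK results are affected.* Samples outside the profile, such as Day 7, also lack a same-day dose. They do not enter the primary parameters, and SAP 5.4.1.2.1 summarizes concentrations at nominal times. The minimum in Cmin is a concentration and needs no hour value.

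The reply does not make the sentence right. It remains the SAP's only PK time formula and disagrees with the protocol. Reading it as the last dose before the sample repairs Days 72 to 84 but ties Day 70 to the Week 8 dose.

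**Conclusion.** The formula in SAP 5.1.1.1.1 is wrong as written for the primary profile: of six samples, four get no time, one (Day 84) is placed about 336 h too early, and one (Day 70) is acceptable. It conflicts with Protocol footnote g and 9.3.1.1.

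This is a low-severity correction of a wrong rule. Literal use would fail visibly, the intended times are recoverable, and no error in AUC0-tau or Cmin is shown. The counts assume the nominal schedule, pre-dose sampling on Days 70 and 84 as footnote f requires, and the same-date reading of the sentence. What the sponsor's NCA guideline says about time after dose is unknown. If it covers the point, the SAP sentence would still need to agree with it.

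**What to change.** Replace the last sentence of SAP 5.1.1.1.1 with:

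> For Visits 8 to 13, relative time (h) = actual sample date/time minus actual Week 10 dose date/time, with the Visit 8 pre-dose sample taken as the start (0 h) and the Visit 13 pre-dose sample as the end of the dosing interval. For all other post-first-dose samples, relative time = actual sample date/time minus the date/time of the most recent dose given before the sample. The Day 0 pre-dose sample is referenced to the first dose.

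Naming both boundary samples matters because SAP 5.1.1.1.3 describes the profile period only as Day 72 to Day 80.

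The cost is one sentence in a SAP amendment and a check that it agrees with the sponsor's NCA guideline. It needs no new data and no change to sampling or dosing.

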#### 5.1.1.1.2 End date of the Treatment Period

*The end date of the Treatment Period will be either the date of Visit 15(Week 24) for study participants completing the Treatment Period, or the date of the Early Discontinuation Visit (EDV) for study participants who discontinued during the Treatment Period. If a participant does not have a Visit 15(Week 24)/EDV, then either the date of the last scheduled or unscheduled visit during the Treatment Period or the date of last known dose of study drug during the Treatment Period, whichever is later, will define the end date of the Treatment Period.*

#### 5.1.1.1.3 Study periods

The duration of the study for each study participant is approximately 38 weeks.; consisting of the following 3 periods:

- Screening Period (up to 28 days): Visit 1, Day -28 to Day -1
- Treatment Period (24 weeks) including Baseline visit: based on the first planned treatment starting from Visit 2 at Day 0 to the last planned treatment on Visit 15 at Day 168 (Week 24)
  - 400mg loading dose phase for doses at Week 0, Weeks 2 and 4 followed by 200mg Q2W maintenance dose phase thereafter (at Week 6, 8, 10, 12, 14, 16, 18, 20, 22 and 24)
  - PK profile treatment Period: Day 72±6 hours to Day 80±6 hours. These visits may be conducted at home visit.
- Safety Follow-Up: The end of study visit will be performed on 70 days after last IMP through SFU visit.

The end of the study is defined as the date of the last visit of the last study participant in the study. Study participants are considered to have completed the study if they complete the last scheduled study visit (Screening, Baseline Visit, Treatment Period [through Week 24], and SFU). The safety follow-up visit is 70 days post last dose. If study participants are continuing onto commercial Cimzia, the safety follow-up is 30 days post last dose.

#### 5.1.1.1.4 Mapping of assessments performed at Early Discontinuation Visit

For time course displays it may be necessary to assign premature withdrawal visits to a specific study time point. In general, premature withdrawal visits should be assigned to what would have been the next scheduled visit for the particular assessment that is being summarized. This re-assignment should be based upon the study day (relative to the baseline visit date). For example, a study assesses anti-CZP antibody sampling at Baseline (Day 0), Weeks 6, 12, 24 and SFU. If a participant discontinues on day 150 of the study, and the previous assessment was done at Week 6, the next scheduled assessment would normally be Week 12. However, study Day 150 is closer to the Week 24 visit (Study Day 168). Therefore, the termination assessment should be re-assigned to the Week 24 visit. If the premature withdrawal visit of study day is tied in the middle of two visits, then earlier visit will be chosen, (assuming earlier visit also without valid datapoint also, to avoid data overwritten). For example, suppose the patient also discontinues at Day 126 ( in the midpoint of Week 24, Day 168 and Week 12, Day 84), then the Week 12, Day 84 will be assigned and firstly considered. However, if there was recently assessed at Week 12, the assessments obtained at

premature termination visit should be re-mapped and analyzed at the Week 24 visit, as there is already valid data available at the Week 12 visit.

Generally speaking, assessments at an Early Discontinuation Visit (EDV) that correspond to a scheduled visit will be summarized at the scheduled visit corresponding to the EDV if the assessment was scheduled to occur at that visit. Such assessments will also be considered for Last Value.

Different domains from the same EDV may be assigned to different visit weeks. For example, the TB questionnaire is scheduled to be collected at screening, Weeks 12, and 24; RAPID3 testing at baseline, and Week 12. If a participant has screening, baseline, and an EDV, both the TB questionnaire and RAPID3 testing withdrawal assessments should map to Week 12.

